2.3 Trial Design, Treatment Conditions, Hypotheses

This two group, 24-week study randomized participants seeking treatment for CUD to either a simultaneous (SIM) or a sequential (SEQ) treatment condition (Figure 1). Urn randomization procedures balanced the conditions on the following baseline characteristics: cannabis abstinence prior to treatment initiation, tobacco dependence severity (low vs. high, based on the Fagerstrom), blunt/spliff smoker or not, ethnicity (African American or not), and gender. Assessments occurred at week 12 (end of Phase 1) and week 24 (end of Phase 2).

2.3.1. SIM Condition. During weeks 1-12 (Phase 1), participants in the SIM condition received immediate access to the previously described CUD and tobacco interventions. The first five CUD MET/CBT modules were completed in a fixed order starting at the first visit. The TI modules and NRT were also available starting at the first visit, but for most participants, this did not occur until the second visit due to time constraints. TI modules could be completed in any order selected by participants, but as per above, NRT was not available until the NRT education module was completed. Both the CUD and TI modules viewed during clinic visits could then be accessed remotely with an ID and password. During weeks 13-24 (Phase 2) SIM participants could continue to access the cannabis and tobacco intervention modules ad libitum remotely but did not attend clinic visits or receive additional NRT. SIM participants that expressed an interest in continuing NRT after Phase 1 were provided with a one-week supply and instructed on how to purchase additional NRT on their own. For those not interested in continuing use, NRT dose was tapered during weeks 10-12 to reduce the probability of nicotine withdrawal symptoms from discontinuation.

2.3.2 SEQ Condition. During Phase 1, SEQ participants received only the CUD MET/CBT/CM intervention. They could not access the TI modules, NRT was not provided by the clinic, and no counseling for tobacco cessation was offered. During their first visit, they were given a booklet on tobacco cessation, *Clearing the Air*

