(<https://www.cancer.gov/publications/patient-education/clearing-the-air>) that provided education and guidelines for quitting and a Quitline telephone number (SIM participants also received the booklet). This reflected “treatment as usual” for tobacco cessation in the context of outpatient treatment for CUD. SEQ participants interested in tobacco cessation during Phase 1 could make cessation attempts but had to obtain tobacco medications on their own. During Weeks 13-24, (Phase 2), SEQ participants were offered the TI as described above, and encouraged to attend weekly clinic visits to help facilitate engagement and adherence. Note that during Phase 2 clinic staff were highly flexible and encouraging of any attendance schedule with the primary goal of accommodating participants so that they could complete TI modules and obtain NRT.

2.3.3 Primary Hypotheses. Based on prior pilot study and the literature on targeting tobacco use in the context of treatment for other SUDs, we hypothesized that: (1) the TI would be acceptable to participants in the SIM condition (i.e., Phase 1 retention and CUD engagement would not differ between conditions, and that the majority of SIM participants would engage with the TI components; (2) during Phase 1, the SIM condition would engender greater use of NRT, more tobacco quit attempts, greater sustained tobacco abstinence than SEQ, and cannabis abstinence would not differ between conditions; (3) at the end of Phase 2, after participants in both conditions were exposed to the TI, a greater percentage of SIM than SEQ participants would have initiated NRT and made a tobacco quit attempt.

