2.4 Measures

2.4.1 Substance Use. At intake, the Substance Use Disorders section of the SCID (First et al., 1995) was administered to determine SUD diagnoses. The timeline follow-back (TLFB) procedure (Sobell and Sobell, 1992) was used to obtain self-reported substance use information for the 90 days preceding intake, and then again at each clinic visit to assess substance use since the last clinic visit. TLFB assessments included cannabis, cigarettes, other tobacco and nicotine products (including smokeless tobacco and electronic cigarettes), alcohol, other drug use, and NRT use. Nicotine dependence was assessed at baseline using the Fagerstrom Test of Nicotine Dependence (FTND; Heatherton et al., 1991).

Cannabis abstinence was verified via twice-weekly observed collection of urine specimens which were then tested immediately thereafter. Cannabis and adulterant testing were performed using dipstick tests with a minimum THC detection cutoff of 50 ng/ml (<http://www.americanscreeningcorp.com>). Failure to submit a specimen without an excused absence was treated as a cannabis-positive result.

Self-reported tobacco abstinence was verified using expired carbon monoxide (CO; coVita Micro + Smokerlyzer: <http://covita.net/micro+.html>). Participants with a CO level ≤ 5 were considered tobacco abstinent. In the event of self-reported tobacco abstinence, a breath CO > 5 , and self-reported cannabis use (which could increase CO level), tobacco abstinence was verified using urine cotinine (ONSCREEN Cotinine Test; <http://www.americanscreeningcorp.com>).

2.5 Outcomes. Primary engagement outcomes included Phase 1 treatment retention defined as clinic attendance, and treatment engagement defined by completion of cannabis and tobacco computer modules, and initiation and duration of NRT. The primary cannabis outcome was the duration of continuous abstinence achieved during Phase 1, assessed using the twice-weekly observed urine specimens. Primary tobacco outcomes included the percent of participants who

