made at least one self-reported tobacco quit attempt during Phase 1, and percent of participants who achieved sustained tobacco abstinence over the final eight weeks of Phase 1. Secondary outcomes included: percent of participants who achieved any biologically-verified cannabis or tobacco abstinence (≥ 1 negative urine THC/cotinine specimen or expired carbon monoxide < 5 ppm), percent of participants who achieved cannabis abstinence throughout the final four weeks of treatment, reduction in percent days of cannabis and tobacco use during treatment relative to baseline, and point-prevalence cannabis and tobacco abstinence at the 12-week follow-up assessment.

2.6 Data Analysis. Sociodemographic and baseline drug use characteristics between treatment conditions were compared using t-tests for continuous measures and chi-square tests for nominal measures (Table 1). The primary cannabis and tobacco abstinence outcomes were analyzed using an intent-to-treat approach with missing biological verification data and dropouts treated as a positive indicator of cannabis or tobacco use. Longest duration of continuous abstinence from cannabis (primary), number of days abstinent from tobacco, and number of tobacco quit attempts (primary) were all zero-inflated and therefore could not be analyzed with models that assume continuous, normally distributed outcomes. We therefore analyzed each of these outcomes using a zero-inflated Poisson model which provides an odds ratio describing the relative likelihood of achieving a zero-response to the outcome in the two treatment arms and a ratio of means describing the relative mean of the outcome in the two treatment groups. Additionally, several binary outcomes were analyzed via chi-square tests: cannabis abstinence in the final 4 weeks, point prevalence abstinence at the end of treatment, achievement of at least 50% reduction in days of using cannabis from intake to the final 4 weeks, and achievement of continuous tobacco abstinence for ≥ 2 consecutive weeks. Phase 2 outcomes were analyzed using descriptive statistics. Statistical comparisons were not made between SEQ Phase 2 and SIM Phase 1 outcomes because of the lack of Phase 2 data due to only a 30% participation rate for SEQ during Phase 2. All analyses were performed using SAS version 9.4.

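### The urine cotinine fallback makes no exception for NRT users, so a true tobacco abstainer on NRT whose CO is raised by cannabis may be scored as a tobacco user; in Phase 1 any such error would fall mainly on SIM.

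*Combined protocol and SAP*

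**What the plan says.** **Verification rule (2.4.1).** CO is the first test, and a value of 5 or less counts as tobacco abstinent. The fallback needs three things at once: self-reported tobacco abstinence, CO above 5 and self-reported cannabis use. The section notes that cannabis can itself raise CO. In that case "tobacco abstinence was verified using urine cotinine". No cotinine cut-off, alternative marker or separate path for NRT users is given. NRT use is recorded on the timeline follow-back (TLFB) at clinic visits, but the rule does not use it.

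**NRT by arm in Phase 1.** SIM could receive NRT from the clinic once the NRT education module was done (2.3.1). For SEQ, 2.3.2 says: "They could not access the TI modules, NRT was not provided by the clinic". It adds: "SEQ participants interested in tobacco cessation during Phase 1 could make cessation attempts but had to obtain tobacco medications on their own". The second hypothesis in 2.3.3 predicts more NRT use in SIM during Phase 1. For SIM participants who did not wish to continue, "NRT dose was tapered during weeks 10-12 to reduce the probability of nicotine withdrawal symptoms from discontinuation".

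**Phase 2.** SIM participants "did not attend clinic visits or receive additional NRT", while SEQ was offered the tobacco intervention, including NRT. Section 2.6 limits Phase 2 to descriptive statistics.

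**Outcomes.** Section 2.5 lists sustained tobacco abstinence in the last eight weeks of Phase 1 as primary. Its secondary outcomes include any biologically verified tobacco abstinence, with a negative cotinine as one qualifying result, and "point-prevalence cannabis and tobacco abstinence at the 12-week follow-up assessment". Section 2.6 adds a chi-square test of "achievement of continuous tobacco abstinence for ≥ 2 consecutive weeks" and a zero-inflated Poisson model of "number of days abstinent from tobacco". It scores absent verification as use.

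**The concern.** The fallback exists to protect true tobacco abstainers from failing CO because they still smoke cannabis, which is a foreseeable event in this population. That protection depends on a marker that NRT can also turn positive. NRT is part of the intervention that separates the arms in Phase 1, so the protection may be weaker in the arm where the plan expects more tobacco abstinence.

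If this happened often enough, verified tobacco abstinence would be under-recorded in SIM relative to SEQ. The error is conservative for a claim that SIM is superior. The risk is the opposite one: concluding that adding the tobacco intervention gave no abstinence benefit when part of the benefit was lost in verification. With 67 participants, a few reclassified people could matter.

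**Working it through.** **Step 1. How the written rule treats a true tobacco abstainer who reports abstinence.**

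| CO | Reports cannabis use | On NRT | Scored as |
|---|---|---|---|
| 5 or less | either | either | abstinent |
| above 5 | yes | no | cotinine test; can be cleared as abstinent |
| above 5 | yes | yes | cotinine test; may be positive from NRT, then a tobacco user |
| above 5 | no | either | no fallback; not abstinent |

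The arms can diverge only between the second and third rows. Compared with CO alone, the fallback adds no failures. It removes some, and removes them unequally.

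The step from NRT to a positive cotinine is general knowledge about the assay, not a statement in the documents. Section 2.1 does class NRT as non-tobacco nicotine. Because no cut-off is given, the third row says may.

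**Step 2. Which outcomes are exposed.**
- Any biologically verified tobacco abstinence (2.5): exposed, because its definition names cotinine. One passing visit is enough, so a person is lost only if every visit fails.
- Sustained abstinence in the last eight weeks (primary in 2.5): exposed. Section 2.6 names no test for it.
- Continuous abstinence for at least two weeks (chi-square in 2.6): exposed.
- Tobacco point prevalence (2.5), read here as the week 12 assessment: exposed. The point-prevalence chi-square in 2.6 names no substance.
- Days abstinent (zero-inflated Poisson in 2.6): exposed only if those days are biologically verified, which the text does not say.
- Quit attempts (primary): self-reported and not exposed.

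**Step 3. Illustration of size.** The documents give no rate of NRT use, of CO above 5 or of fallback use, so every input here is an assumption. For true SIM abstainers, let:
- u = share on NRT, 0.4 to 0.8
- c = share still smoking cannabis without tobacco, 0.3 to 0.7 (blunt or spliff smokers are not counted as true abstainers)
- q = chance of CO above 5 at one check, 0.1 to 0.3

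Cotinine is taken to be always positive on NRT.

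Share misclassified at a single check = u × c × q:
- low: 0.4 × 0.3 × 0.1 = 0.012
- middle: 0.6 × 0.5 × 0.2 = 0.060
- high: 0.8 × 0.7 × 0.3 = 0.168

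This gives 1.2% to 17%. For week 12 the upper end may be too high, because the taper could lower u or the cotinine level in those not continuing NRT.

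For the contrast between arms, assume 0 to 0.2 of SEQ abstainers buy their own NRT. The excess in SIM is (u_SIM − u_SEQ) × c × q:
- low: (0.4 − 0.2) × 0.3 × 0.1 = 0.006
- high: (0.8 − 0) × 0.7 × 0.3 = 0.168

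In people, assume 33 in SIM (about half of 67; the text gives no arm sizes) and a true abstinence rate of 20%. That is 33 × 0.20 = 6.6 true abstainers. Then 6.6 × 0.012 = 0.08 and 6.6 × 0.168 = 1.11, so about 0.1 to 1.1 people. The recorded rate would be 20% × (1 − 0.012) = 19.8% down to 20% × (1 − 0.168) = 16.6%.

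I give no figure for the eight-week outcome. It would need a CO schedule and a rule for how many failed checks break sustained abstinence. The twice-weekly schedule in 2.4.1 is for urine cannabis testing, not CO.

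**The case against.** The strongest reply is that nothing shows an effect. A visit is affected only when reported tobacco abstinence, CO above 5, reported cannabis use, current NRT and a positive cotinine all coincide. Staff may have applied an exception that this condensed text does not record. On the single-check illustration, about one person or fewer is affected. All of this stands, and it keeps the point to a request for clarification, a count and a conditional analysis.

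A second reply is that classifying flagged visits by self-report drops verification exactly where CO failed, which could favour SIM, including through tobacco in blunts or spliffs. That also stands. It is why such an analysis can only be a sensitivity analysis.

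Three stronger readings are tempting, and the documents do not support them:
- A reader might infer that NRT users were generally scored as tobacco users. They were not: CO of 5 or less passes regardless of NRT.
- A reader might infer that the tobacco comparison is in fact biased against SIM, perhaps by a large share of abstainers. No visit of this kind is documented, and larger figures depend on an assumed CO schedule and scoring rule.
- A reader might infer that SEQ is free of the problem. SEQ participants could obtain NRT themselves, so the Phase 1 imbalance is one of degree. By week 24 the clinic supply had moved to SEQ, but Phase 2 is only described.

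Neither reply removes the gap: applied as written, the rule can treat two true abstainers differently because of NRT, and clinic NRT differed by arm.

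**Conclusion.** The point holds as a gap in the written verification rule. Applied as written, 2.4.1 can score a true abstainer on NRT as a tobacco user when cannabis has raised CO, while the same person not on NRT can be cleared. In Phase 1 any such error would fall mainly on SIM and would understate, not create, a SIM tobacco benefit. This rests on the text of 2.4.1, the NRT provisions in 2.3.1 and 2.3.2, and the general fact that cotinine derives from nicotine.

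Whether it happened, and how often, cannot be learned from the documents. The illustrative 1.2-17% shows only that, under the assumed inputs, the effect could range from negligible to material. A cheap clarification is warranted; a conclusion that the results are biased is not.

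**What to change.** 1. State how cotinine-positive visits of NRT users were actually scored.
2. Using the TLFB NRT records, by the same rule in both arms, count by arm the visits and participants with all five features: self-reported tobacco abstinence, CO above 5, reported cannabis use, NRT use and positive cotinine.
3. Keep the written rule as the primary analysis.
4. If any visit is flagged, add a sensitivity analysis, labelled post hoc, of the verified tobacco outcomes with flagged visits classified by self-report. Note that this could favour SIM.
5. If the two analyses differ, say that a conclusion of no tobacco benefit is not robust to the verification rule.

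The cost is some wording, one count table and, if needed, one re-derivation from TLFB, CO and cotinine data already collected. No new assay is required. If no visit is flagged, one sentence closes the point.

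Two minor wording matters nearby are separate from the NRT point and should be reconciled:
- The CO cut-off is ≤ 5 in 2.4.1 and < 5 in 2.5, so a reading of exactly 5 passes one and fails the other.
- Section 2.4.1 scores only unexcused missed urine specimens as positive, whereas 2.6 scores all missing verification data as positive. State which rule governs the primary cannabis run length.

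### Sections 2.5 and 2.6 disagree on the primary tobacco outcomes: the eight-week abstinence outcome has no named test, and the quit-attempt count, not the percentage, is labelled primary

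*Combined protocol and SAP*

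**What the plan says.** Section 2.5 (Outcomes) names two primary tobacco outcomes, each a percentage of participants: those who "made at least one self-reported tobacco quit attempt during Phase 1", and the "percent of participants who achieved sustained tobacco abstinence over the final eight weeks of Phase 1". Its secondary list includes, for cannabis, the "percent of participants who achieved cannabis abstinence throughout the final four weeks of treatment". It does not list a two-week tobacco outcome.

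Section 2.6 (Data Analysis) makes three relevant statements.

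- Analysis set: "The primary cannabis and tobacco abstinence outcomes were analyzed using an intent-to-treat approach", with missing verification and dropout counted as use. This sentence names no test.
- Count outcomes: the primary label is attached to the "number of tobacco quit attempts (primary"), analysed with a zero-inflated Poisson model. The model is said to give an "odds ratio describing the relative likelihood of achieving a zero-response to the outcome in the two treatment arms", plus a ratio of means.
- Binary outcomes: "several binary outcomes were analyzed via chi-square tests: cannabis abstinence in the final 4 weeks", followed by point-prevalence abstinence, a reduction of at least 50% in cannabis days, and "achievement of continuous tobacco abstinence for ≥ 2 consecutive weeks".

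In section 2.3.3, hypothesis 2 predicts more quit attempts and more sustained tobacco abstinence in SIM without fixing a metric. Hypothesis 3, for the end of Phase 2, frames quit attempts as a percentage.

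**The concern.** The main problem is the eight-week outcome. It is declared primary, yet 2.6 never mentions it. The chi-square list finds room for a secondary cannabis outcome and for a tobacco outcome that 2.5 does not declare, but leaves this primary out. The outcome is also undefined: 2.5 writes *throughout* for four-week cannabis abstinence but *over* for eight-week tobacco abstinence, so a reader cannot tell whether one lapse is a failure.

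The lesser problem is the quit-attempt metric: a percentage in 2.5 and a count in 2.6. The count model returns two estimates, and neither is named as the primary result.

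What is at stake is the tobacco part of hypothesis 2, because a reader cannot say which result is confirmatory. Section 2.6 is written in the past tense and describes observed distributions, so a change made after seeing the data cannot be ruled out. Nothing in the documents shows one, and inconsistent drafting is equally possible.

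**Working it through.** **Step 1. The two sections side by side.**

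| Item | 2.5 | 2.6 |
|---|---|---|
| Quit attempts, Phase 1 | Primary, percent with any | Labelled primary as a count; zero-inflated Poisson |
| Abstinence, final eight weeks | Primary, percent | No test named; reached only by the intent-to-treat sentence |
| Abstinence run of at least two weeks | Not listed | Chi-square; no window, no label |
| Cannabis abstinence, final four weeks | Secondary | Chi-square |

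The plan gives no figure to reproduce: there is no alpha, power, assumed rate or allocation ratio. The only relevant number is the 67 enrolled (146 − 53 − 15 − 11 = 67).

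**Step 2. How the two-week outcome relates to the eight-week one.** Treat each of the 12 Phase 1 weeks as abstinent or not, giving 2^12 = 4,096 patterns. These are counts, not probabilities, and the weekly grid is a simplification. They establish direction only.

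- Abstinent throughout weeks 5–12: weeks 1–4 are free, so 2^4 = 16 patterns.
- A run of at least two weeks anywhere: 377 patterns have no such run, so 4,096 − 377 = 3,719.
- A run of at least two weeks inside weeks 5–12: 201 of the 256 eight-week patterns qualify, so 201 × 16 = 3,216.
- Patterns that pass only through a run starting before week 5: 3,719 − 3,216 = 503.

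Every pattern that meets either reading of the 2.5 outcome also meets the two-week rule without a window. The reverse fails for 3,703 patterns (3,719 − 16) on the first reading and 503 on the second. With all 67 in the denominator and the same missing-data rule, the two-week rate therefore equals or exceeds the declared rate. If the two-week test were confined to weeks 5–12, it would match the second reading.

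**Step 3. Whether the zero part of the model can stand in for the percentage.** In a standard zero-inflated Poisson model with excess-zero share π and Poisson mean λ, P(any attempt) = (1 − π)(1 − e^−λ). The zero part compares π/(1 − π) between arms, not the observed share with no attempt. All π and λ below are assumed; odds ratios are SIM relative to SEQ.

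| SEQ π, λ | SIM π, λ | Any attempt, SEQ vs SIM | OR, observed zero | OR, zero part |
|---|---|---|---|---|
| 0.3, 1 | 0.3, 2 | 44% vs 61% | 0.52 | 1.00 |
| 0.5, 1.5 | 0.3, 1.5 | 39% vs 54% | 0.53 | 0.43 |
| 0.3, 1 | 0.4, 2 | 44% vs 52% | 0.74 | 1.56 |

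Row 1 in full: 0.7 × (1 − e^−1) = 0.442 and 0.7 × (1 − e^−2) = 0.605; observed-zero OR = (0.395/0.605)/(0.558/0.442) = 0.52; zero-part OR = (0.3/0.7)/(0.3/0.7) = 1.00. The zero part misses the difference in row 1, agrees in row 2 and reverses in row 3.

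**Step 4. What a direct comparison can deliver.** Assume a 33/34 split. At 44% vs 61%, the 95% half-width for the risk difference is 1.96 × √(0.442 × 0.558/33 + 0.605 × 0.395/34) = 0.236, about 24 percentage points. The smallest expected count in the abstinent row is 33 × 10/67 = 4.93 with 10 abstinent and 33 × 11/67 = 5.42 with 11, so it falls below 5 if 10 or fewer are abstinent.

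**The case against.** The best reply on the main point is that the test may be there under another description. If the declared outcome means a two-week run inside the final eight weeks, and the chi-square item is confined to those weeks, the two coincide and only a definition is missing. The change from *throughout* to *over* leaves this open. The support is thin, however: 2.6 gives the two-week item neither a window nor a primary label, and 2.5 does not mention a two-week run. A reader should not have to infer the primary test.

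On quit attempts, hypothesis 2 suits a count, and 2.6 evidently means the odds ratio for zero response to address any versus none. That intent is visible and makes this the weaker part. The examples in step 3 are assumed, and the reversed case needs SIM to have both more excess zeros and a higher mean. The model's ratio of Poisson means, 2.0 in rows 1 and 3, would still favour SIM. What stands is that the label differs between sections, the model gives two answers without ranking them, and agreement with the declared percentage cannot be relied on.

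It is also true that pattern counts say nothing about likelihood, and that 2.6 states its missing-data rule only for primary abstinence outcomes. Handling that is more lenient for the two-week outcome, with all 67 kept in the denominator, would only raise its rate further relative to the eight-week one.

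**Conclusion.** The concern holds and needs correction. Section 2.6 names no test for one declared primary tobacco outcome and analyses the other on a different metric; no other section reconciles them. The first part carries the weight; the second alone would be a labelling fault.

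The effect on the trial's results cannot be sized, because no tobacco outcome rates are given. The direction finding rests on the two-week run being allowed anywhere in Phase 1 and on all 67 participants being counted. The point about the model rests on the standard zero-inflated Poisson form. Neither shows that outcomes were switched.

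**What to change.** Amend 2.5 and 2.6 so that they name the same outcomes.

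- Define the eight-week outcome: abstinent throughout weeks 5–12, or a stated minimum run within them. Compare that percentage between arms in all 67 participants, with missing counted as use.
- Compare the percentage with any Phase 1 quit attempt between arms in all 67. Participants with no recorded attempt, including dropouts, count as having made none.
- Use the plan's chi-square test, or an exact test where expected counts are small, and report each risk difference with its 95% confidence interval.
- Label the two-week outcome and the attempt count secondary or post hoc. Alternatively, if the primaries were changed, state when and why.

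The cost is wording plus two 2×2 analyses on data already collected. The intervals will be wide, as step 4 shows, and the eight-week result may be less favourable than the two-week one.

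### Scoring missing data as use is not automatically conservative for the hypothesis that cannabis abstinence does not differ, and no other missing-data analysis is named

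*Combined protocol and SAP*

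**What the plan says.** Section 2.3.3 lists, among the primary hypotheses for Phase 1, that "cannabis abstinence would not differ between conditions". It also expects that "Phase 1 retention and CUD engagement would not differ between conditions".

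Section 2.5 states: "The primary cannabis outcome was the duration of continuous abstinence achieved during Phase 1", measured from the twice-weekly observed urines. Section 2.6 analyses it with a "zero-inflated Poisson model which provides an odds ratio describing the relative likelihood of achieving a zero-response to the outcome", together with a ratio of means. It adds that "several binary outcomes were analyzed via chi-square tests: cannabis abstinence in the final 4 weeks".

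On missing data, section 2.6 applies an intent-to-treat approach to the primary abstinence outcomes, with missing verification and "dropouts treated as a positive indicator of cannabis or tobacco use". Section 2.4.1 has a narrower rule for urines: "Failure to submit a specimen without an excused absence was treated as a cannabis-positive result". How a specimen missed with an excuse is scored is not stated.

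The documents give no margin for the no-difference hypothesis, no Phase 1 missingness by arm and no second missing-data analysis.

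**The concern.** Counting missing as use is usually defended as cautious because it makes a treatment benefit harder to show. For cannabis the hypothesis here runs the other way: the trial hopes to show that adding the tobacco intervention does no harm. For such a claim, an analysis that moves the arms closer together makes the hoped-for conclusion easier to reach.

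Equal retention, the situation the trial itself expected, is also the situation in which the rule compresses the absolute difference if dropout is unrelated to use. With no alternative analysis planned, the conclusion on a primary hypothesis rests on one untested assumption.

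**Working it through.** **Inputs.** From the documents: 67 enrolled (section 2.1) and one missing-data rule for both arms (section 2.6). The text gives no arm sizes, so 33 SIM and 34 SEQ are assumed. It gives no abstinence rate, Phase 1 dropout rate or margin, so there is no design figure to reproduce. Assumed: true abstinence pSIM = 0.20 and pSEQ = 0.40, a 20-point margin, and dropout d of 0 to 50% unrelated to abstinence within arm. The example is a binary outcome, such as abstinence in the final four weeks.

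**Step 1: equal dropout.** Under missing = use, observed rate = p(1 − d).
- At d = 0.40: SIM 0.20 × 0.60 = 0.12; SEQ 0.40 × 0.60 = 0.24.
- Difference: −0.20 becomes −0.12, that is, multiplied by (1 − d).
- Odds ratio: (0.20/0.80)/(0.40/0.60) = 0.375 becomes (0.12/0.88)/(0.24/0.76) = 0.43.
- Risk ratio: 0.20/0.40 = 0.12/0.24 = 0.50, unchanged.

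**Step 2: unequal dropout.** Observed difference = pSIM(1 − dSIM) − pSEQ(1 − dSEQ). A true deficit shrinks only if pSIM × dSIM < pSEQ × dSEQ; here, only if SIM dropout is below twice SEQ dropout.
- SIM 45%, SEQ 30%: 0.11 − 0.28 = −0.17 (still shrunk).
- SIM 55%, SEQ 20%: 0.09 − 0.32 = −0.23 (enlarged).
- No true difference (40% in both arms), SIM 45%, SEQ 30%: 0.22 − 0.28 = −0.06 (a false deficit).

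If everyone who dropped out was in fact using, the imputed values are correct and there is no bias.

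**Step 3: effect on a confidence interval.** Enumerate all pairs of binomial counts at 33 and 34, and sum the probability that the 95% interval for the difference (unpooled standard error) lies wholly above −0.20 when the true deficit is 20 points.

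| Dropout, each arm | Observed SIM / SEQ | Wrongly excludes a 20-point deficit |
|---|---|---|
| 0% | 20% / 40% | 2.6% |
| 20% | 16% / 32% | 6.3% |
| 30% | 14% / 28% | 9.6% |
| 40% | 12% / 24% | 14.9% |
| 50% | 10% / 20% | 23.4% |

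The fair comparator at 40% dropout is another analysis of the same incomplete data. Completers only (0.60 × 33 and 0.60 × 34, about 20 per arm) give 2.9%. The rise to 14.9% is therefore bias from the rule and not lost sample size.

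A non-significant chi-square is a different matter: 56.0% with complete data, 74.6% under missing = use, but already about 71% in completers.

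**Step 4: the primary duration outcome.** A simulation of the longest abstinent run over 24 visits (12 weeks × 2) assumed 40% SIM and 60% SEQ ever abstinent and 5% of specimens missed intermittently.

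| Dropout SIM / SEQ | Zero-response odds ratio, true → imputed | Ratio of overall means, true → imputed |
|---|---|---|
| 30% / 30% | 2.26 → 2.02 | 0.67 → 0.67 |
| 50% / 50% | 2.23 → 1.86 | 0.67 → 0.67 |
| 30% / 50% | 2.25 → 1.50 | 0.67 → 0.82 |
| 50% / 30% | 2.24 → 2.50 | 0.67 → 0.55 |

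At 30% in both arms the mean difference moves from −1.54 to −1.07 visits.

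**The case against.** A reader might infer that the rule necessarily shrinks a SIM deficit and so favours the hoped-for result. The documents do not support that. The only participation figure is for SEQ in Phase 2, which does not bear on the Phase 1 cannabis outcome. If the added tobacco programme drove SIM participants out, the rule could work against the hypothesis, as the 55% versus 20% case shows.

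A reader might also blame the rule for the rise in non-significance from 56% to 75%. Most of that is lost information, which no imputation restores: completers alone give about 71%.

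Other objections have force:
- **Scale.** With equal dropout the risk ratio and the ratio of overall means do not move. Of the primary model's two outputs, only the zero-response odds ratio is drawn toward 1, and modestly.
- **Plausibility.** Incentives were paid for cannabis-negative urines (section 2.2.1), so a missed visit may well signal use. Missing = use would then be right, and missing-at-random imputation could overstate abstinence.
- **Scope.** The rule does not cover all missing data. Section 2.6 ties it to the primary abstinence outcomes, and section 2.4.1 exempts excused absences.
- **Margin.** The plan states no margin and no decision based on a confidence interval; the 20 points are this review's assumption.
- **Retention.** Phase 1 attendance is a primary outcome (section 2.5), so unequal dropout would be examined, though no table of missing specimens is specified.

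These points limit the claim to a conditional one. They do not remove the gap: the conclusion depends on why specimens are missing, and nothing planned tests that.

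**Conclusion.** The point holds in conditional form. For the cannabis hypothesis, missing = use can bias toward no difference on the difference and odds-ratio scales when dropout is unrelated to use and similar or lower in SIM. It can bias the other way when SIM dropout is sufficiently higher, and it is unbiased if those who dropped out were using. Which of these applied cannot be told from the documents.

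Under the assumptions above, wrong exclusion of a 20-point deficit rises from 2.6% to between 6% and 23% as equal dropout goes from 20% to 50%. These figures illustrate a binary outcome and do not estimate what happened in this trial. The remedy is worth making because a primary conclusion is at stake and no other missing-data analysis is named.

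**What to change.** - Keep missing = use as the main analysis.
- For the Phase 1 cannabis outcomes, including duration of continuous abstinence, add one named sensitivity analysis: multiple imputation of missing urine results from arm, site, baseline use and earlier results. Shift the imputed values toward use in steps, so that missing at random and missing = use form the two ends of the range.
- Tabulate missing specimens by arm, excused and unexcused separately, and state how excused absences are scored, so that sections 2.4.1 and 2.6 agree.
- Report the between-arm difference with a 95% confidence interval under each assumption. If the results diverge, describe the no-difference conclusion as dependent on the missing-data assumption.

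The cost is one extra analysis and one table on existing data. The small downside is that the second result may weaken the claim.
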